4.6 Data Rules

Dates:

Generally, for each date stored in the database a set of organizational variables will be derived in order to describe the temporal context of that date in the specific study in terms of: the phase of treatment (pre, during or post study treatment), the day relative to the start of study treatment, the day relative to the end of study treatment.

Year will be calculated as (days/365.25) rounded up to 1 decimal place.

Month will be calculated as (days/30.44) rounded up to 1 decimal place.

Time to event or duration of event endpoints will be based on the actual date rather than Visit Day.

Baseline:

Unless specified otherwise, baseline is the last pre-dose measurement performed prior to the first administration of the first study drug.

Post-Baseline:

Every value taken after the Baseline measurement is considered a post-Baseline value.

Change from Baseline:

Change from baseline is defined as (post-baseline value - baseline value).

Indirect Bilirubin:

Indirect Bilirubin is calculated as:

$$\text{total Bilirubin} - \text{direct Bilirubin}$$

Indirect Bilirubin was entered in the CRF at the beginning of the study. These values will not be analyzed and only presented in the subject data listings for completeness. Summary statistics will only be created from the derived indirect Bilirubin as per formula given above.

Unscheduled Visits:

Unscheduled Visits will not be used in the analysis (i.e. section 14) and will only be presented as part of the subject data listing (i.e. section 16).

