9.4.5 Other Safety Analyse(s)

For all safety analyses, the FAS will be used as the FAS definition matches the one of the safety set. The incidence of TEAE (new or worsening from baseline) will be summarized by system organ class and preferred term, severity (based on CTCAE grades), type of AE and relation to study treatment. Deaths reportable as SAEs and non-fatal serious AEs will be listed by participant and tabulated by type of AE. AEs leading to study treatment discontinuation and/or modifications will be summarized. Laboratory abnormalities will be summarized by severity. Frequency and incidence rates will be provided. Frequency tables will also be provided for changes in severity from baseline to worst value post-baseline. Laboratory data considered as AE will be graded according to CTCAE v. 5.0, if applicable. The following summaries will be generated separately for hematology and biochemistry, overall and by cohort with the same dose:

- Frequency table for newly occurring on-treatment all CTCAE grades and CTCAE Grades 3 or 4
- Shift tables using CTCAE grades to compare baseline to the worst on-treatment value

CCI

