6.5.5 Clinical laboratory data

Descriptive statistics (number of observations, mean, standard deviation, minimum, median and maximum values) will be presented for clinical laboratory tests (hematology, clinical biochemistry and urinalysis), their changes from baseline (including baseline value), and their percent changes from baseline at applicable visits.

Severity of hematological and biochemical laboratory values will be assessed based on NCI CTCAE Version 5.0. CTCAE severity grading for laboratory abnormalities are based on applicable laboratory threshold values outlined in NCI CTCAE. It should be noted that in the present analysis of those laboratory parameters for which additional clinical information potentially can also influence the toxicity grade, this clinical information is in general not available and only the laboratory measurements are used for severity assessment.

Any additional specific handling of the NCI CTCAE toxicity grading assignments will be noted in the footnotes of the corresponding tables as applicable per the data collection in the study.

- In the event of overlapping CTCAE criteria ranges for specific lab tests, the algorithm assigns the worst grade
- If calcium type is not recorded (i.e. only “calcium” is recorded), then grading is done as if the calcium is total calcium. “Calcium corrected” is computed from total calcium and serum albumin (if ≤ 4.0 g/dl) from the same time point based on CTCAE v5.0 guidance. If serum albumin (if ≤ 4.0 g/dl) from the same time point is not available or if “calcium, unspecified” was collected then grading is done as if the calcium is “corrected calcium.”
- Results with special characters (such as “>” and “<”) are not graded.

The frequency of treatment emergent laboratory abnormalities regarding hematology, coagulation panel, clinical chemistry, and urinalysis will be tabulated. Worst grades for hematological and biochemical toxicities will be calculated according to CTCAE based on laboratory measurements, and will be summarized by NCI CTCAE category and worst grade.

Clinical laboratory toxicities during treatment including a period of 30 days after last dose of treatment will be considered as “treatment-emergent” for Regorafenib. The duration for Nivolumab will be 100 days.

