The last non-missing value before or on the first day of study drug will be retained as “baseline” data. If several assessments are performed on the same day (without timing information) the average of the values will be considered.

Incidence tables (frequency and percentage of patients) as well as tables with change in NCI CTCAE worst grade from baseline will be presented as following:

- Hematological and biochemical toxicity during screening (the last evaluation available before assignment to treatment is taken into account).
- Treatment-emergent hematological and biochemical toxicity.
- Treatment-emergent hematological and biochemical toxicities with incidence rate above 5% in any treatment arm.
- Change in worst grade for hematological and biochemical toxicity from baseline.

The laboratory values will be also categorized into low, normal and high according to their reference ranges.

Descriptive statistics will be calculated by time interval.

Unscheduled laboratory data will be listed (Section 16 of the CSR) only.

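### The SAP keeps unscheduled lab and ECG results out of every table, so the worst-grade, shift and threshold tables can understate a patient's worst value

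*SAP*

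**What the plan says.** SAP 4.6 sets a general rule: "Unscheduled Visits will not be used in the analysis (i.e. section 14) and will only be presented as part of the subject data listing". SAP 6.5.5 repeats it for labs: "Unscheduled laboratory data will be listed (Section 16 of the CSR) only". SAP 6.5.6 has the same sentence for ECGs. None of the three makes an exception.

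The tables governed by the rule include several built on a patient's most extreme value:

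- In SAP 6.5.5: "Worst grades for hematological and biochemical toxicities will be calculated according to CTCAE based on laboratory measurements"; "Change in worst grade for hematological and biochemical toxicity from baseline"; and "Treatment-emergent hematological and biochemical toxicities with incidence rate above 5% in any treatment arm".
- In SAP 6.5.5.1: counts of ALT or AST above 3, 5, 10 and 20 x ULN, of bilirubin and ALP elevations, of concurrent ALT/AST and bilirubin elevations, and of abnormal TSH classified by FT3/FT4.
- In SAP 6.5.6: counts of QTc above 450, 480 and 500 msec, and of increases above 30 and 60 msec.

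Protocol 9.4.5 asks, for hematology and biochemistry, for "Shift tables using CTCAE grades to compare baseline to the worst on-treatment value". It also asks for tables of severity change from baseline to the worst post-baseline value. Neither request is limited to scheduled visits.

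**The concern.** A maximum taken over scheduled visits alone is not the worst value on treatment. The omission is also not random. Much unscheduled safety testing is done because something is already abnormal, so the excluded results come mainly from patients under closer watch.

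At stake is the descriptive safety picture of the combination, above all liver toxicity. A patient could appear at too low a CTCAE grade or x ULN row, or be absent from a count if the only qualifying value was unscheduled. Worst lab grades come from the measurements and AE grades from the investigator, so the lab tables could also disagree with the AE tables and listings. The primary ORR test is not affected.

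**Working it through.** The plan gives no figure for this point to reproduce. The check compares the rules with the schedule.

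**1. Direction.** Let S be a patient's scheduled values in the window and U the unscheduled ones. Then max(S) ≤ max(S and U together). Adding U can leave a worst grade or threshold count unchanged or raise it, never lower it. (For parameters where low is abnormal, the same holds with the minimum.)

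**2. Scheduled chemistry** (protocol 1.3, Schedule of Activities): D1, D8, D15 and D22 in cycle 1; D1, D8 and D15 in cycle 2; D1 only from cycle 3; then EoT and the follow-up visits.

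**3. Additional tests the protocol calls for.**
- Table 6-6 footnote: liver tests at least weekly after a listed event with dose interruption or modification, until values recover or settle.
- Table 6-6 footnote on re-escalation: twice a week for 2 weeks, then weekly for at least 4 weeks.
- Section 8.2.4: repeats of clinically significant abnormal values.

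**4. Weekly liver tests off the schedule.** A 28-day cycle holds 4 weekly tests. Off-schedule = 4 − scheduled:

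| Cycle | Scheduled | Off-schedule |
|---|---|---|
| 1 | 4 | 0 of 4 |
| 2 | 3 | 1 of 4 (25%) |
| 3 onward | 1 | 3 of 4 (75%) |

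**5. Re-escalation checks.** 2 × 2 + 4 × 1 = 8 checks over 6 weeks (42 days). Two full stable cycles must come first, so this falls in cycle 3 or later, where D1 is the only scheduled on-treatment draw. One or two D1 visits can fall in 42 days, leaving 6 to 7 of 8 off-schedule. This monitoring follows a discretionary decision, and the footnote is attached to one row of Table 6-6 only.

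**6. Thyroid rows.** SAP 6.5.5.1 looks for FT3/FT4 within 2 weeks after an abnormal TSH. On treatment, thyroid tests are scheduled on D1 from cycle 2. With ±3-day windows the shortest gap is 28 − 3 − 3 = 22 days, which exceeds 14. Apart from the same draw or an EoT visit, a follow-up test inside the window would be unscheduled.

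**7. ECG.** As the Schedule of Activities row reads, ECGs are at screening and EoT, so EoT is the only scheduled post-baseline ECG. Protocol 7.1 foresees QTcF findings after enrollment in participants who may continue. An on-treatment ECG done for clinical reasons would not enter the QTc counts.

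**8. What one patient can do at n = 70** (hypothetical: a patient with no qualifying scheduled value).
- Above-5% table: 4/70 = 5.7% is shown; 3/70 = 4.3% is not.
- Rare row: 1/70 = 1.4%, exact 95% upper limit 7.7%; 0/70 has an upper limit of 5.1%.

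**The case against.** The strongest reply is that only by-visit summaries were meant. In SAP 6.5.5 the exclusion directly follows a line on statistics by time interval, and protocol 9.4 leaves the treatment of missing and unused data to the SAP. Both points are fair. But SAP 4.6 covers all Section 14 output, and a programmer following it would drop these values everywhere. Leaving data handling to the SAP does not turn a scheduled-only maximum into the worst value.

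It could also be said that the SAP contradicts itself, since 4.6 states "Every value taken after the Baseline measurement is considered a post-Baseline value" and 6.5.5 defines treatment-emergence by time: "Clinical laboratory toxicities during treatment including a period of 30 days after last dose of treatment". This is weak: a definition of post-baseline and a rule on which records enter tables can coexist.

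Several limits on the concern stand:

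- If the triggering value came from a scheduled draw, the patient is already in that row. Follow-up tests can then only raise the grade or the row, and above 20 x ULN there is no higher ALT/AST row.
- The above-5% table is a subset of the full treatment-emergent table, so a toxicity missing from it still appears there if any scheduled value qualifies.
- Protocol 6.6.2 calls for weekly re-evaluation during a nivolumab delay but does not order laboratory tests, so it adds nothing to the count.
- Clinically relevant lab and ECG findings are to be recorded as AEs. The SAP plans AE tables by worst grade and for high bilirubin and liver enzymes, counts new clinically significant ECG abnormalities, and lists all values. The liver AE tables, however, depend on the finding having been entered as an AE.

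**Conclusion.** The concern holds as a rule that is wrong as written. For the CTCAE worst-grade and shift tables it conflicts with protocol 9.4.5. The x ULN, thyroid, above-5% and QTc-threshold counts are affected by the same rule. A reader might infer that they too breach protocol 9.4.5, but that section names none of them; they are defined in the SAP.

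A reader might also infer that toxicity will be under-reported, or that 75% of peaks will be missed. The documents support neither. The shares are of tests, not of peaks or patients, and assume that tests outside the Schedule of Activities are stored as unscheduled visits. The SAP does not define that term. How many patients need such tests, and how often the peak falls on one, is not given. What can be said is that these tables could understate the worst value and cannot overstate it by leaving results out. The ECG point rests on reading the schedule row as screening and EoT only.

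This should be fixed before the tables are produced. It does not bear on the efficacy conclusion.

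**What to change.** In SAP 4.6, 6.5.5 and 6.5.6, limit the exclusion of unscheduled data to by-visit and by-interval descriptive summaries. Add that all laboratory and ECG results in the treatment-emergent window (30 days after the last regorafenib dose, 100 days after the last nivolumab dose), scheduled or unscheduled, are used for the worst-grade, shift, above-5% incidence, x ULN, thyroid and QTc-threshold tables. SAP 6.5.6 states no window for ECGs, so the sentence should say that the same one applies.

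The cost is minor SAP wording and table reprogramming. No new data collection is needed: the SAP already lists unscheduled values, and protocol 8.2.4 requires non-protocol lab results that are clinically significant or change management to be recorded in the eCRF. Reported lab and QTc toxicity may look slightly less favourable.

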4.1.3 Active Follow-Up

A mandatory clinical visit to monitor safety will take place 30 d (window of +7 d) after the last administration of regorafenib/nivolumab and 100 d (window of +7 d) after the last dose of nivolumab. Longer safety FU for nivolumab is required due to the long half-life of the antibody.

Participants who discontinue study intervention due to radiologically progressive disease will terminate the active FU period after the clinical safety visits.

Participants, who have not progressed clinically or radiologically or have discontinued study intervention for reasons other than death, withdrawal of consent or lost to FU, will continue with radiological tumor assessments. During the active follow-up period, CT (computed tomography) /MRI (magnetic resonance imaging) evaluations will be performed at the same intervals as during study treatment (every 8 weeks for the first year, and thereafter, every 12 weeks). In addition, study intervention-related toxicity/AE and information about survival status and subsequent anti-cancer therapy will be followed up until completion of the active FU.

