Tumor assessments will be performed locally by participating radiologists/Investigators and whenever possible all scans taken at each clinical site will be interpreted by the same radiologist/Investigator at that site. Scans must meet the standard of care for imaging of lesions in the respective organ system(s). Unless progression is noted, all lesions will be assessed and reported at each scheduled scan.

All imaging scans (coded with study participant number and in digital imaging and communications in medicine [DICOM] format) as well as imaging-related adjunctive data (e.g., fluorodeoxyglucose [FDG] dose and tracer uptake time) must be prospectively collected and transferred to Bayer, or Bayer-designated imaging core lab, in case independent central review is needed.

The tumor markers CEA and CA 19-9 will be evaluated on an exploratory basis in participants with CRC and will not be used to assess objective tumor response.

Assessment of disease

RECIST v1.1 will be applied by the Investigator as the primary measure for categorization of disease on the baseline imaging and assessment of tumor response until progressive disease (see Section 10.7). CR and PR must be confirmed with repeated imaging performed at least 4 weeks after initial documentation of response.

iRECIST is based on RECIST v1.1, but adapted to account for the unique tumor response seen with immunotherapeutic drugs. iRECIST will be used by the Investigator to assess tumor response and progression, and make treatment decisions (see Section 10.8).

Tumor scans are required at screening, during study treatment and at the End of Treatment: see section 1.3 SoA Table 1–2. Tumor scans are also required during active follow-up, if applicable.

- Baseline assessments will be conducted during the screening period and target lesions should to be selected, measured, and recorded before start of study intervention. Scans that were obtained prior to the participant signing the ICF document for this study can be used as baseline assessments provided that they were performed within 28 d of starting study treatment and meet the requirements for the study

- Assessments during study treatment will be performed every 8 weeks (± 7 d) for the first year and every 12 weeks ± 14 d thereafter. Tumor assessment during the study intervention period includes the same anatomic areas as baseline and will be done until radiological disease progression or the end of the study.

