- Radiological tumor evaluation (within 14 days after last study treatment is not necessary if the previous tumor evaluation was performed within 4 weeks (for the first year) or within 8 weeks (thereafter)).
- For participants who discontinue study treatment without disease progression, FU tumor evaluations will be performed until progression of malignancy and/or start of subsequent systemic anti-cancer treatment, whichever comes first, or any other criterion for withdrawal is met. During the active FU period, CT/MRI evaluations will be performed at the same intervals as during study treatment.
- At the Investigator's discretion, tumor scans may be repeated at any time if progressive disease is suspected. For further details, see Sections 10.7 and 10.8.

For participants who show evidence of radiological PD by RECIST v1.1 and are clinically stable, the Investigator will decide whether to continue a participant on study treatment until repeat imaging is obtained using iRECIST for participant management. Participant must be re-consented for continuation of treatment beyond initial documentation of disease progression (If repeat imaging does not confirm PD per iRECIST (iCPD), as assessed by the Investigator, and the participant continues to be clinically stable, study treatment may continue and follow the regular imaging schedule. If PD is confirmed (iCPD), participants will be discontinued from study treatment).

Treatment beyond confirmed progression as per iRECIST is possible if the participant is still benefiting from treatment after documented discussion and approval by the Sponsor.

When clinically stable, participants should **not** be discontinued until progression is confirmed by the Investigator, working with local radiology, according to the rules outlined in Section 10.8. This allowance to continue treatment despite initial radiologic PD takes into account the observation that some participants can have a transient tumor flare in the first few months after the start of immunotherapy, and then experience subsequent disease response. This data will be captured in the clinical database.

For treatment beyond progression as per iRECIST the following needs to be fulfilled:

- Evidence of clinical benefit as assessed by the investigator
- Absence of symptoms and signs indicating unequivocal progression of disease.
- Absence of clinical signs or symptoms of progression despite a rising CEA level.

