4.3 Handling of Missing Data

All missing or partial data will be presented in the subject data listing as they are recorded on the Case Report Form (CRF).

The number of subjects who prematurely discontinue the study and study treatment for any reason, as well as the reasons for premature discontinuation of study and study treatment, will be reported.

Missing or unevaluable tumor assessments, including scheduled assessments that were not done and incomplete assessments that did not result in an unambiguous tumor response evaluation according to RECIST 1.1, will not be used in the calculation of derived efficacy variables related to tumor assessments unless a new lesion occurred or the lesions that were evaluated already showed progressive disease. No imputation will be performed for missing lesion assessments and tumor response evaluation.

If a date is incomplete, (e.g. only year and month of date of tumor assessment or date of death is available), then day 15 of the month will be used for the calculation of, for example, overall survival and progression free survival. For imputation of AE dates, if the range of possible dates (e.g. a month, if day is missing) and during this time period “treatment emergent” and “non treatment emergent” is possible, the date will be imputed such that the AE will be “treatment emergent” (e.g. the day of treatment start if day is missing).

If the actual scan date of the radiological progression is missing and radiological or clinical progression has been documented based on criteria specified in the protocol, the scheduled scan date will be used to calculate the time to progression.

Safety variables, medical history and concomitant medications:

Treatment emergent AEs, treatment phases, period and relative days will be derived according to data management programming, the operations manual and standard guidelines.

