6.2.3 Secondary endpoints

Overall survival (OS):

Overall survival is defined as the time (days) from the date of first treatment to the date of death.

OS for subjects who are still alive and in the study or who are lost to follow-up at the point of analysis will be censored at the last available date.

OS for subjects who have no post baseline information will be censored at day 1.

Progression free survival (PFS):

PFS is defined as the time (days) from the date of first treatment to the date of radiological or clinical disease progression or death due to any cause, if death occurs before progression is documented.

PFS for subjects without radiological or clinical tumor progression or death at the time of analysis will be censored at their last date of tumor evaluation.

PFS for subjects who have no tumor assessment post baseline and are still alive will be censored at day 1. Patients that report a PD after missed tumor assessment(s) will be censored at the last scan date the patient was known to be progression free.

Disease control rate (DCR):

Disease control rate is defined as the proportion of patients whose best response was complete response (CR), partial response (PR) or stable disease (SD). DCR will be evaluated at 8, 16, 24, 32 and 40 weeks

Scans collected after first progression disease (PD) will not be considered.

Duration of response (DOR):

Duration of response (for PR and CR) is defined as the time (days) from the first documented objective response of PR or CR, whichever is noted earlier, to disease progression or death (if death occurs before progression is documented). Duration of response will be defined for responders only, i.e. subjects with CR or PR.

Time to response (TTR):

Time to response is defined as the time (days) from first treatment until CR or PR and will be derived for responders only.

Duration of stable disease (DoSD):

[figure not shown]

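### SAP 4.6 keeps unscheduled visits out of all analyses with no exemption for tumor assessments; read literally, it can discard progressions seen only on extra scans and bias PFS and DOR upward

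*SAP*

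**What the plan says.** The rule stands in SAP 4.6 (Data Rules), under General Statistical Considerations: "Unscheduled Visits will not be used in the analysis (i.e. section 14) and will only be presented as part of the subject data listing". It names no data type and carries no exception. The same section says "Time to event or duration of event endpoints will be based on the actual date rather than Visit Day".

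The protocol produces scans away from the regular schedule in two ways:

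- Regular imaging is "every 8 weeks for the first year, and thereafter, every 12 weeks" (Protocol 4.1.3; the on-treatment interval in 4.1.2 and 8.1 is the same). Protocol 8.1 adds that, at the investigator's discretion, "tumor scans may be repeated at any time if progressive disease is suspected".
- Protocol 8.1 also requires that "CR and PR must be confirmed with repeated imaging performed at least 4 weeks after initial documentation of response".

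An end-of-treatment scan will not always follow. Protocol 8.1 says it "is not necessary if the previous tumor evaluation was performed within 4 weeks (for the first year"), with a longer allowance after the first year.

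SAP 6.2.3 counts radiological or clinical progression, or death, as a PFS event. Without an event, PFS is censored at the last tumor evaluation, and "PFS for subjects who have no tumor assessment post baseline and are still alive will be censored at day 1". SAP 6.2.2 defines ORR as the percentage with CR or PR and does not mention confirmation. Neither section mentions unscheduled scans.

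**The concern.** An exclusion of unscheduled visits is ordinary for by-visit tables of laboratory values, ECGs or vital signs, where extra measurements distort the visit means. It does not suit endpoints defined by the first occurrence of an event. An extra scan made because progression is suspected is more likely than a routine scan to show progression. Removing it removes events selectively and leaves the patient counted as progression-free for longer than the data show.

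PFS and DOR are secondary endpoints and carry much of the supporting efficacy description in this open-label, single-arm, investigator-assessed study. With no exemption written down, two programmers could also derive different PFS and DOR values from the same database, and the choice could be made after the results are known.

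**Working it through.** **1. Does any text exempt tumor scans?**

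- SAP 4.6, actual-date sentence: it fixes which date is used for an assessment that is in the analysis. It does not say which assessments are in.
- SAP 4.3: it covers missing or unevaluable assessments, which are not used "unless a new lesion occurred or the lesions that were evaluated already showed progressive disease". A complete scan at an unscheduled visit is neither missing nor unevaluable.
- SAP 6.2.2 and 6.2.3: silent.
- SAP 6.5.5, 6.5.6 and 6.5.8: each repeats a listing-only rule, for laboratory, ECG and vital-sign data. If 4.6 covered only those data, it would be redundant.

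No exemption is written.

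**2. What happens to a progression seen only at an unscheduled visit?**

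| What follows | PFS under a literal reading |
|---|---|
| Clinical progression also recorded | Event kept, at that date |
| Treatment continues and a later scheduled scan shows PD | Event kept, but later |
| Death with no usable PD record | Event kept, but later |
| None of these | Censored at the last scheduled scan, or at day 1 if there is none |

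The SAP states no censoring rule for DOR; I assume the same handling.

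**3. What happens to a response?** A week-8 response can be confirmed by the week-16 scan, which is 8 weeks later and so meets the 4-week minimum. A scan at week 12 falls on a cycle visit: 3 cycles × 28 days = 84 days = 12 weeks, so week 12 is C4D1. The Schedule of Activities lists D1 of every cycle from 3 onward as a visit. A response is therefore lost only if its sole first or confirming scan was at an unscheduled visit. For confirming scans, the loss also requires that the protocol's confirmation rule is applied.

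**4. The plan's own figures.** With N = 70, at least 8 responders, null 5% and target 17% (SAP 6.2.1 and 6.2.2), the exact binomial gives:

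- Type I error: P(X ≥ 8 | 70, 0.05) = 0.0234, within the stated limit of 2.5%.
- Power: P(X ≥ 8 | 70, 0.17) = 0.9256, against 92.6% stated. It reproduces.

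**5. Illustrative size for PFS.** Assumptions, none from the documents: exponential PFS with median m = 8, 16 or 24 weeks; a share u of progressions seen only at unscheduled visits; no recovery by clinical progression, a later scan or death; 8-weekly scans.

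The probability of progressing within one 8-week interval is p = 1 − 2^(−8/m). With all scans used, 24-week PFS is (1 − p)³. With the unscheduled ones dropped, each such patient is censored at the preceding scheduled scan, so the hazard at each scan is (1 − u)p / (1 − up) and 24-week PFS is [(1 − p)/(1 − up)]³.

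| m (weeks) | p | All scans used | u = 10% | u = 20% |
|---|---|---|---|---|
| 8 | 0.500 | 12.5% | 14.6% | 17.1% |
| 16 | 0.293 | 35.4% | 38.7% | 42.4% |
| 24 | 0.206 | 50.0% | 53.2% | 56.7% |

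A simulation under the same assumptions gives 0.125 → 0.145 and 0.171; 0.349 → 0.383 and 0.420; 0.503 → 0.535 and 0.569. The rise is about 2 to 3 points at u = 10% and 5 to 7 points at u = 20%.

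**6. Illustrative size for ORR.** If a share q of true responders lost their only qualifying scan, the observable target rate would be 0.17 × (1 − q). For q = 5%, 10% and 20% that is 0.1615, 0.153 and 0.136, and power falls from 92.6% to 89.6%, 85.9% and 75.2%. The documents give no value for q, and step 3 suggests that it is small.

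**The case against.** The best defence is that the rule was meant for by-visit safety tables. It speaks of visits, not scans; its repetitions are all in the safety sections; and SAP 4.3 keeps a progression even when the assessment is incomplete, or when its scan date is missing. A plan that does this is unlikely to intend throwing away a complete scan that shows progression. This is a fair reading of intent, but the text of 4.6 does not say it.

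Three stronger readings are tempting and not supported:

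- **Every progression on an extra scan is lost.** PFS also counts clinical progression and death. Under Protocol 8.1 and 10.8, clinically stable participants may stay on treatment after first progression and are imaged again. Some events are recovered, although a later scan or a death still moves the date later.
- **Responses confirmed at 4 weeks drop out of ORR.** Being off the 8-week scan schedule is not the same as being at an unscheduled visit; the week-12 scan falls on C4D1. SAP 6.2.2 does not itself require confirmation, and the next 8-week scan can supply it.
- **The primary test is in danger because one responder decides it.** The exact one-sided p-values are 0.0234 for 8/70 and 0.060 for 7/70. They describe the boundary of the test, not how often this rule would remove a responder.

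**Conclusion.** The concern holds in limited form. SAP 4.6 is general and unqualified, and following it literally can discard a progression recorded only at an unscheduled visit. The main harm is an upward bias in PFS and DOR, both descriptive and untested. ORR is exposed only to a narrow risk of losing responses, which would lower the observed rate.

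The size cannot be established from the documents. The 2 to 7 points on 24-week PFS rest on an assumed 10% to 20% of progressions being affected, assumed medians of 8 to 24 weeks, and no recovery by clinical progression, later scans or death. Recovery would reduce the bias. The direction for PFS and DOR is firmer than the size, because the protocol ties these extra scans to suspected progression.

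**What to change.** Add to SAP 4.6, before database lock:

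> This rule does not apply to tumor assessments; all scans, scheduled or not, are used at their actual date for best overall response and its confirmation, DCR, DOR, DoSD, TTR and PFS.

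Keep the unscheduled-visit exclusion for by-visit summaries only, including the by-visit RECIST display in SAP 6.2.2.

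The cost is one sentence. No new data are needed, since SAP 4.6 already sends unscheduled visits to the subject listings. The design is unchanged: 8 of 70 responders, exact type I error 2.34%, power 92.6%. If the sponsor always meant the rule for by-visit tables, the sentence records that intent.
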